### **13. Use of Cloud Computing Services**

- Cloud computing services will NOT be used in this study.
  - Cloud computing services WILL be used in this study as described below and have been approved nationally by the VA Chief Information Officer (CIO). (Note: ONLY cloud computing services that have been approved nationally may be used.)

## PROTOCOL

Neurosteroids as Novel Therapeutic Agents for PTSD in OEF/OIF/OND Veterans  
PI: [name], PhD

### Data Analysis and Statistical Considerations

The analysis plan is organized around the study's hypotheses using a variety of statistical techniques. Univariate summary statistics, including means, medians, rates, proportions, and variances, will be calculated as appropriate for all variables. In addition to statistics, outcome measures will be examined graphically to assist in determining distributional form as a precursor to model selection. Preliminary bivariate analyses by treatment condition will use standard Chi-square procedures for categorical outcomes; continuous outcomes meeting distribution requirements will be tested using Student's t-test, whereas data not meeting distributional requirements will be analyzed by nonparametric (e.g., Kruskal-Wallis) procedures. Differences between covariates will be tested at baseline to assess randomization. Putative covariates with significant asymmetry between groups will be considered for inclusion in subsequent modeling and testing (However, see Miller & Chapman, 2001). Inference for all analyses will be evaluated relative to  $p=0.05$  within a given hypothesis.

Analysis of primary outcomes in the Shifted-Attention Emotion Appraisal (SEAT) Paradigm will present compound stimuli that include both emotional faces (e.g. sad, happy, angry) and neutral scenes (Sripada et al 2014). In three different conditions, participants will be asked to respond to three different questions: (1) 'Gender': Whether the face in the foreground is male or female; (2) 'Inside/Outside': Whether the scene in the background is indoors or outdoors; or (3) 'Like/Dislike': Whether the face in the foreground is liked or disliked. This allows multiple components of cognition to be probed including (1) implicit emotional processing, (2) attentional modulation, and (3) cognitive modulation of emotion. Item-specific memory will be tested first using yes/no recognition judgments. The conjunctive memory test will require participants to make "match" (previously viewed faces and buildings presented in a combinations seen during encoding) or "mismatch" (items in combinations not previously seen together) judgments.

For fMRI analysis we will use FSL supplemented by BIRN tools for signal averaging, ROI analysis, and visualization of time series waveforms (Smith SM 2004). We use FreeSurfer for surface reconstruction and automatic segmentation. FMRIB Software Library (FSL) preprocessing will be used for motion correction, slice time correction, temporal and spatial filtering, and co-registration with the individual subject's high resolution anatomical image. A first level analysis will be performed on each run separately using a standard GLM approach with regressors determined by the task timing convolved with a delayed canonical hemodynamic response. The first level analyses from a subject will then combined in a fixed effects second level analysis. These second level analyses are then combined into between group third level analyses using a mixed effects model. The functional MRI data will be analyzed by comparing whole brain voxelwise neural activity (BOLD) associated with cognitive processing between pre- and post-treatment, between active and placebo arms, between-face types (e.g. angry, fearful, neutral), and between-task conditions (e.g. gender, indoor/outdoor, like/dislike), which is neurosteroid relevant (Sripada et al 2013a, Sripada et al 2013b). [name] was the

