Several groups of investigators have reported that serum DHEA and/or DHEAS levels are altered in PTSD (Kanter 2000; Spivak et al., 2000; Sondergaard et al., 2002, and Rasmussen et al., 2004; Yehuda et al., 2006). Possibly contributing to somewhat mixed findings, prior studies contained relatively small numbers of participants with PTSD (the largest study reports findings for 52 participants with PTSD), and few studies controlled for age and smoking in their analysis plans (two critical co-variates). In contrast, our DHEAS findings support the current project include 213 OEF/OIF/OND Veterans with PTSD, controlling for age and smoking (we report DHEAS levels in a total over 660 OEF/OIF/OND Veterans). It has been hypothesized that greater DHEA release following ACTH administration may represent a compensatory response to severe stress (Rasmussen et al 2004). In a small sample of untreated Israeli male combat Veterans with chronic PTSD, higher plasma DHEA and DHEAS levels were observed in comparison to healthy male control subjects without PTSD (Spivak et al., 2000); however, it is unknown if DHEA and/or DHEAS levels were correlated with PTSD symptoms specifically in that investigation. Perhaps even more importantly, serum DHEAS levels are positively associated with resilience in several recent studies (Petros et al., 2013; Radant et al., 2001, Taylor 2013), and a series of innovative investigations in Special Forces also support the concept that DHEAS is associated with enhanced resilience (Morgan et al 2009, 2004). It is thus possible that treatment with DHEA has the potential to increase resilience among OEF/OIF/OND Veterans with PTSD. Although difficult to quantify as a variable that is sensitive to change, initial studies suggest that the Connor-Davidson Resilience Scale (CD-RISC) may be a useful tool to begin to understand the construct of resilience (Davidson et al 2008), as the neurobiological underpinnings of resilience continue to be elucidated (McEwen et al 2015, Russo et al 2012). Recent neuroimaging evidence also supports a possible role for DHEA in the treatment of PTSD. Specifically, efforts in collaboration with investigators at the University of Michigan ([name] and [name]) demonstrate that *one-time DHEA administration (400 mg orally) appears to alter functional connectivity between the amygdala and the hippocampus (Sripada et al 2013, 2014)*, brain regions that are implicated in the pathophysiology of PTSD. *In*

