### **Selection of Subjects**

Forty OEF/OIF/OND Veterans with PTSD between the ages of 18-65 will be randomized. Both male and female subjects and all ethnic groups will be eligible to participate in this study. All subjects will be currently experiencing PTSD, as evidenced by a CAPS-5 score that is  $\geq 33$  at baseline. We chose a CAPS-5 score of  $\geq 33$  after review of the available limited literature on this area. For example, a recent poster presented at the American College of Neuropsychopharmacology (ACNP) provided for rationale on use of CAPS-5 score of  $\geq 29$  for non-combat PTSD vs  $\geq 33$  for combat PTSD (Sullivan, G et al., 55th Annual Meeting; ACNP, December 7, 2016). We anticipate that a number of participants will have co-occurring depression symptoms and a history of mild TBI (mild TBI and major depression are not exclusionary); we will thus control for the presence of major depression and a history of mild TBI in the statistical analysis. Patients who have a history of moderate or severe TBI will be excluded. Veterans will be recruited from the Durham VA Medical Center and VA Mid-Atlantic MIRECC Repository and Post-deployment Health Study in OEF/OIF/OND Veterans. This Repository has enrolled over 3,200 OEF/OIF/OND Veterans to date, and

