Change in total DSM5-defined PTSD symptoms from pre- to post- treatment, as assessed by the CAPS-5, the gold standard method for assessing PTSD symptoms in pharmacological treatment trials; measurements will be gathered at two-week intervals beginning at baseline and continuing through Week 8. Measures of pre-post treatment differences at the four study intervals will be regressed on a dichotomous proxy measure denoting treatment status coded positive for subjects randomized to the DHEA condition. In addition to the treatment proxy, all models will include covariates for measurement interval (time), and an interaction term crossing the treatment proxy with time. Test of the secondary hypothesis will be based on a 1 df test of the contrast of difference between drug and placebo at the final time point (SAS: LSMESTIMATE statement). Specifically at Week 8, H0: LSMEdhea  $\geq$  LSMEplacebo versus Ha: LSMEdhea  $<$  LSMEplacebo. We hypothesize rejection of a null hypothesis positing that difference in PTSD symptoms from baseline will be equivalent or greater among subjects randomized to DHEA at the final time point in lieu of an alternative hypothesis positing a reduction in PTSD symptoms in the DHEA cohort relative to placebo.

Measures of serum levels of three neurosteroids: DHEA, DHEAS, and androsterone will also be analyzed. As above, the outcome measure will be the change in steroid level from baseline (i.e., following 2 week placebo lead in) to Week 8 with measurements at two-week intervals. Models will be estimated as described above with tests of the primary hypothesis based on a 1 df test of the estimated contrast of the difference between drug and placebo at the final time point. In all cases, the following hypothesis will be tested: H0: LSMEdhea  $\leq$  LSMEplacebo versus Ha: LSMEdhea  $>$  LSMEplacebo. Results for tests of Aim 2 will be adjusted for multiple comparisons using the method of Hochberg (1998).

As secondary test of the hypothesized association between change in PTSD status and change in neurosteroid levels, Week 8 changes CAPS-5 scores will be regressed on Week 8 change in neurosteroid levels. Models will include, as above, covariates for age, gender, smoking status, depression, TBI status, and a measure of the baseline level of the tested neurosteroid. Based

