## PROTOCOL

### Neurosteroids as Novel Therapeutic Agents for PTSD in OEF/OIF/OND Veterans

PI: [name], PhD

on anticipated collinearities between the dichotomous randomization proxy and change, models will initially be estimated without the former. A significant inverse association between change in steroid levels and change in CAPS-5 scores would support the hypothesized efficacy of DHEA as an adjunctive therapy in treating PTSD. As above, results would be corrected for multiple comparisons.

Tests of secondary measures will be conducted as described above. Thus, proposed measures will be regressed as change from baseline scores on a model controlling for the baseline level of the tested outcome measure, the dichotomous randomization proxy, and an interaction term crossing the latter with time. Tests will again be based on a 1 df test of the estimated contrast (LSME: see above) of the difference between drug and placebo at the final time point. Expectations are that change in adverse outcome measures will be significantly mitigated in the DHEA intervention arm; measures associated with salubrious outcomes will be, conversely, improved. All results will be adjusted for multiple comparisons.

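### The adjustment set for the clinical models is left to baseline significance tests, and the depression and mild TBI control promised elsewhere is not in the listed CAPS-5 model

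*Combined protocol and SAP*

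**What the plan says.** Five statements bear on which covariates enter the clinical models.

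- Data Analysis and Statistical Considerations, opening paragraph: "Differences between covariates will be tested at baseline to assess randomization". The next sentence reads "Putative covariates with significant asymmetry between groups will be considered for inclusion in subsequent modeling and testing", followed by a parenthetical caution that cites a source. The candidate covariates are not listed.
- Selection of Subjects, after noting that depression and mild TBI are expected and not exclusionary: "we will thus control for the presence of major depression and a history of mild TBI in the statistical analysis". No imbalance condition is attached.
- Same analysis section, CAPS-5 paragraph: change is regressed on treatment, and beyond that "all models will include covariates for measurement interval (time), and an interaction term crossing the treatment proxy with time". Depression, TBI and baseline CAPS-5 are not named.
- Same section, regression of CAPS-5 change on neurosteroid change: "Models will include, as above, covariates for age, gender, smoking status, depression, TBI status", plus the baseline neurosteroid level. The sentence points back to an earlier list, but the section contains none.
- Same section, closing paragraph on secondary measures: change scores are regressed on "a model controlling for the baseline level of the tested outcome measure", treatment and its interaction with time. Secondary Outcome Measures names CAPS-5 change first among the secondary outcomes.

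Randomisation is described as blocks of 4, with no stratification mentioned.

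**The concern.** Under sound randomisation any baseline difference between arms is chance. Its p-value therefore says nothing about whether the covariate predicts outcome, which is what determines whether adjusting for it helps. With 16 per arm the test misses imbalances large enough to move the estimate, and it sometimes picks variables that do not matter.

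The rule also leaves the model open. Being considered for inclusion is not a decision rule, and with no candidate list two analysts could follow the plan and fit different CAPS-5 models. One might fit treatment, time and interaction alone. Another might add baseline CAPS-5 from the closing paragraph, depression and TBI from Selection of Subjects, or all five covariates from the association model. At stake are the prespecification of the main clinical comparison and, possibly, precision from baseline data that the trial already collects.

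**Working it through.** **1. Sample size.** The Design section gives 40 randomised and 20% drop-out: 40 × (1 − 0.20) = 32, or 16 per arm. This reproduces the plan's 32. The analysis section's 10% would give 36; that is a separate inconsistency. The plan refers to power calculations but shows no effect size, SD, R² or power, so those inputs below are assumptions.

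**2. What the baseline test detects** (two-sided 0.05, df = 30).
- Power against a true 0.5 SD difference, noncentral t with ncp = 0.5/√(2/16) = 1.41: 28%.
- Observed difference needed for a flag: 2.042 × √(2/16) = 0.72 SD. An observed 0.5 SD difference gives t = 1.41, p = 0.17, and is not flagged.
- If the covariate correlates 0.5 to 0.6 with the outcome, that unflagged 0.5 SD imbalance shifts the unadjusted estimate by 0.5 × 0.5 = 0.25 to 0.5 × 0.6 = 0.30 outcome SDs.
- Binary example, assuming 16 of 32 have major depression: a 10 v 6 split gives uncorrected χ² = 2.0, below 3.84. An 11 v 5 split (χ² = 4.5) is needed for a flag.
- With five independent candidates (the number of subject characteristics in the association model), the chance of at least one false flag is 1 − 0.95⁵ = 22.6%. With two it is 9.8%.

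**3. Power.** Simplified to one final time point with no missing data, 16 per arm, d = 0.9 (assumed), normal covariates. The CAPS-5 hypothesis is directional, so the test is taken as one-sided at 0.05. Always-adjusted power uses noncentral t with df = 30 − k and ncp = d/√[(1 − R²) × (29/(29 − k)) × 2/16]. The test-then-adjust column is simulated, 40,000 trials per setting. Unadjusted power is 80%.

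| Covariates | R² | Test-then-adjust | Always adjusted |
|---|---|---|---|
| 1 (r = 0.2) | 0.04 | 80% | 80% |
| 1 (r = 0.3) | 0.09 | 80% | 82% |
| 1 (r = 0.5) | 0.25 | 81% | 88% |
| 1 (r = 0.6) | 0.36 | 82% | 92% |
| 3 | 0.04 | 79% | 77% |
| 3 | 0.09 | 80% | 79% |
| 3 | 0.25 | 80% | 86% |

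Two-sided, one covariate at r = 0.5 to 0.6 gives about 70% against 80–86%. On this formula three covariates break even with the unadjusted test at R² of about 0.11. At d = 0.8 the break-even was about 0.075 for two covariates and 0.185 for five.

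**4. What baseline CAPS-5 could contribute.** With equal variances and baseline–final correlation ρ, ANCOVA variance is (1 + ρ)/2 of the change-score variance, so R² for change is (1 − ρ)/2: 0.25 at ρ = 0.5, 0.15 at ρ = 0.7, 0.10 at ρ = 0.8. Baseline CAPS-5 alone would therefore cover the cost of all three covariates up to ρ of about 1 − 2 × 0.11 = 0.78. The r = 0.6 row would need ρ = 1 − 2 × 0.36 = 0.28, so it is an optimistic upper end for this covariate.

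**5. Type I error.** In simulations under no effect, test-then-adjust gave one-sided rates of about 0.043–0.047 at R² of 0.2 to 0.4, against a nominal 0.05.

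**The case against.** The best defence is that the plan does not make the test the sole way in. The association model names its covariates outright, and the closing paragraph adjusts for the baseline outcome. Because CAPS-5 is listed as a secondary outcome, that adjustment can fairly be read as covering it. The back-reference in the association model suggests the authors believed depression and TBI already applied to the preceding models. The CAPS-5 sentence says what the models will include, not that they include nothing else. The selection rule is soft and carries its own caution, and it uses baseline data, not outcomes.

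Most of this stands, and it rules out some stronger readings. A reader might infer that covariates enter only after a significant baseline test, or that baseline CAPS-5 is definitely left out; the text supports neither. A reader might also infer that the rule inflates false positives; the simulation shows it slightly conservative. Nor is a loss of power certain, since the table shows no gain at r = 0.2 and a loss with three weak covariates.

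What the defence does not do is settle the model. It relies on a list that is not there and on one of two readings of the closing paragraph, and the unconditional promise in Selection of Subjects still conflicts with a rule that depends on observed imbalance.

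**Conclusion.** The point holds as a prespecification fault in secondary clinical analyses. The selection rule is a poor one, it conflicts with the promise on depression and mild TBI, and the listed CAPS-5 terms do not deliver that promise. None of this depends on an assumed effect size.

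The precision argument is secondary and conditional. Under d = 0.9 and one covariate at r = 0.5 to 0.6, fixed adjustment gains about 7–11 points of one-sided power (about 81% to 88–92%). At r = 0.2 to 0.3 it gains 0–2 points. The simulation ignores repeated measures and missing data, so it gives the order of the effect and not a forecast. The validity of the test is not in question, and the primary fMRI outcome is outside this point.

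**What to change.** 1. Delete the sentence that makes covariates candidates when a baseline test is significant. Whether the baseline table then carries p-values is a reporting preference and not part of this point.
2. For the CAPS-5 model and the other clinical outcome models, state one fixed set, whatever the observed imbalance: the baseline value of that outcome, major depression and mild TBI history. Name the visit that supplies the baseline value.
3. Reconcile Selection of Subjects with the analysis section's opening, CAPS-5, association-model and closing paragraphs. Replace the back-reference with an explicit list, and say whether the closing paragraph governs CAPS-5.

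Keep the set short. Carrying the five-covariate list into the CAPS-5 model would need R² of about 0.185 to break even with 32 patients.

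The cost is SAP wording, settled before unblinding, with no new data or visits. The statistical price is three degrees of freedom, or about 2–3 points of power if total R² is only about 0.04.

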### Design

This is a parallel-group, double-blind, placebo (PBO)-controlled, randomized Phase 2 pilot study using adjunctive dehydroxyepiandrosterone [DHEA (400 mg)] will be evaluated to establish Proof of Concept (POC) for this agent in OEF/OIF/OND Veterans with PTSD.

Aim 1. To determine the effects of an acute oral administration of adjunctive DHEA (400 mg) on neuroimaging measures of functional connectivity. We will conduct a parallel-group, double-blind, placebo (PBO)-controlled, randomized Phase 2 pilot study with one-time oral DHEA 400 mg in target engagement. To establish POC, we seek to determine if DHEA is superior to PBO in target engagement of neural circuits related to fear-anxiety-emotion regulation using the shifted-attention emotion appraisal (SEAT) paradigm (see below). Following a two-week placebo lead-in period (all participants), subjects will be randomized to receive a one-time oral dose of adjunctive DHEA (400mg) or PBO. Neuroimaging will occur 2 hours following drug administration for peak level effects on target engagement of fear-anxiety emotion circuit connectivity, as previously conducted by Sripada, [name], [name] et al.).

Primary Outcome Measure The primary outcome measure will be functional connectivity between amygdala-hippocampus assessed using fMRI based SEAT Paradigm as a target engagement endpoint. The fMRI based SEAT Paradigm has been previously validated to an acute administration of DHEA (400 mg) in healthy volunteers by members of my career development team, Drs. [name] and [name] (Sripada et al., 2013).

Aim 2. To evaluate a sustained 6-week adjunctive DHEA treatment compared to PBO on PTSD symptoms severity (CAPS-5), co-occurring depression (BDI), and other secondary outcome measures such as resilience (CD-RISC). Following randomization to acute DHEA administration or PBO the subject will continue to receive study drug for 6 weeks (for DHEA, fixed escalating doses: 100 mg per day in divided doses x 1 week, followed by 200 mg per day in divided doses x 1 week, followed by 400 mg per day in divided doses x 4 weeks).

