## PROTOCOL

Neurosteroids as Novel Therapeutic Agents for PTSD in OEF/OIF/OND Veterans  
PI: [name], PhD

and fMRI. We estimate that approximately 80% of all participants enrolling in the proposed randomized controlled trial will also receive neuroimaging to an acute administration of DHEA or PBO placebo and post-treatment with DHEA or PBO. We thus anticipate that approximately 32 or more participants will undergo neuroimaging to an acute treatment with DHEA or PBO and at study completion (a minimum of approximately 16 participants per group in this pilot POC study). Susceptibility tensor imaging is a new methodology created by our collaborator at Duke, [name].

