## PROTOCOL

Neurosteroids as Novel Therapeutic Agents for PTSD in OEF/OIF/OND Veterans

PI: [name], PhD

whether buildings are indoors or outdoors; or (3) 'Like/Dislike': whether the face is liked or disliked. This task probes emotion regulation: (1) implicit emotional processing, (2) attentional modulation of emotion, and (3) modulation of emotion by appraisal. The 'Gender' condition probes implicit emotional processing, as attention is focused on an emotional face while identifying its gender, and it is established that negative emotional faces induce negative emotions. The 'Inside/Outside' condition engages attentional modulation of emotion as in focusing attention on the building components superimposed on the emotional face. Attention modulation is recognized as a core component of emotion regulation. The 'Like/Dislike' condition engages cognitive appraisal of one's emotional/evaluative state and engaging appraisal increases activation of dorsal medial prefrontal cortex ([name] et al, 2000; Phan et al, 2004). Behavioral studies of emotional appraisal find that this strategy lowers distress (Lieberman et al, 2011). The ability of DHEA to impact functional connectivity between the amygdala and hippocampus in healthy volunteers undergoing the SEAT paradigm will be evaluated in Veterans with PTSD to an acute target engagement dose of DHEA (400 mg) and following a sustained 6-week treatment.

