### Study Interventions

We will conduct a parallel-group, double-blind, placebo (PBO)-controlled, randomized Phase 2 pilot study with 400mg DHEA to test whether we can establish proof of concept (POC) for this agent. 40 OEF/OIF/OND Veterans with PTSD will be randomized to receive a one-time oral adjunctive treatment with DHEA or PBO in the fMRI paradigm (same day). Participants will then continue to receive a 6-week sustained treatment of DHEA or PBO. To establish POC, we seek to determine whether DHEA is superior to

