### **Costs and/or Payments to Subjects**

Participants will be reimbursed \$75 for each study visit plus an additional \$100 for each MRI. Therefore, if they participate in all 5 study visits and 2 MRIs, they will receive \$575. There will be an additional allowance based on distance traveled by the participant. For ease of calculation, concentric zones will be used as summarized in the table below.

Distance (miles)	Allowance	Typical towns and cities
0-25	\$10	Raleigh, Durham, Cary, Chapel Hill
25-50	\$20	Henderson, Wake Forest, Burlington
50-100	\$30	Greensboro, Fayetteville, Goldsboro
100-150	\$35	Salisbury, Greenville, Rocky Mount

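### No scan precedes the first randomised dose, so a pre- to post-treatment imaging change compared between arms estimates the Week 8 effect minus the acute effect

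*Combined protocol and SAP*

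**What the plan says.** **Timing of the first scan.** Under Design, Aim 1: "Following a two-week placebo lead-in period (all participants), subjects will be randomized to receive a one-time oral dose of adjunctive DHEA (400mg) or PBO". It continues: "Neuroimaging will occur 2 hours following drug administration for peak level effects on target engagement". Study Interventions agrees that dose and scan share a day: participants are "randomized to receive a one-time oral adjunctive treatment with DHEA or PBO in the fMRI paradigm (same day").

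**Number of scans.** The MRI row of the Schedule of Events is marked at Week 2 (Visit 2) and Week 8 (Visit 5) only. The payment section gives the total for a participant "if they participate in all 5 study visits and 2 MRIs". The Exploratory Aim describes the same pair: participants "will undergo neuroimaging to an acute treatment with DHEA or PBO and at study completion". Randomised drug continues for the 6 weeks between them.

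**What is to be compared.** The first objective, under Purpose, compares pre- to post-treatment change in amygdala-hippocampal connectivity between DHEA and placebo. Data Analysis and Statistical Considerations describes "comparing whole brain voxelwise neural activity (BOLD) associated with cognitive processing between pre- and post-treatment" and then lists, as further comparisons, active versus placebo, face types and task conditions. The primary ANOVA in the same section has factors for drug, face type and condition, and none for time. The description of the SEAT task says connectivity will be evaluated "to an acute target engagement dose of DHEA (400 mg) and following a sustained 6-week treatment". Nowhere is it stated which scan counts as pre-treatment, or which scan the active versus placebo comparison uses.

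**The concern.** A change score compared between arms estimates a drug effect only if the first measurement is free of the drug. Here the first scan is timed to the peak drug level in the DHEA arm. For the one-time dose, which is the primary objective, there is no earlier scan to subtract, so the objective cannot be carried out as written. For the 6-week question, the only available change is Week 8 minus Week 2, and subtracting Week 2 removes the acute effect from the sustained one.

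At stake is how the imaging result is read. A null or negative change contrast could be taken as absence of target engagement when DHEA raised connectivity at both scans. The larger the acute effect that the trial hopes to find, the further the change contrast falls below the sustained effect.

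**Working it through.** **1. Scan count.** The payment section gives $75 per visit, $100 per MRI and a total of $575. With 5 visits and k MRIs:
- k = 1: 5 × 75 + 100 = 475
- k = 2: 5 × 75 + 200 = 575
- k = 3: 5 × 75 + 300 = 675

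Only k = 2 reproduces the stated total, in agreement with the Schedule of Events.

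**2. Imaging sample.** 40 × 0.80 = 32, or 16 per arm, as the Exploratory Aim states.

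**3. What the change contrast estimates.** Let m2 and m8 be the expected connectivity at Weeks 2 and 8 without drug. Randomisation makes these equal across arms. Let a be the drug effect 2 hours after the first dose and s the drug effect at Week 8.
- DHEA change: (m8 + s) - (m2 + a)
- Placebo change: m8 - m2
- Difference between arms: s - a

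A pre/post comparison within the DHEA arm alone is no better: it gives (m8 - m2) + (s - a), which adds the time trend.

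**4. Direct arm comparisons.** At Week 2: (m2 + a) - m2 = a. At Week 8: (m8 + s) - m8 = s. Each estimates the quantity of interest.

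**5. Simulation of the change contrast.** The documents give no effect size, SD or between-scan correlation for connectivity. Assumed: SD 1 at each scan; correlation 0.3, 0.5 or 0.7; 16 per arm; one outcome; two-sided t-test at 0.05; 40,000 trials per setting.

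| a (SD) | s (SD) | Mean change contrast | Rejection rate, change contrast |
|---|---|---|---|
| 0.5, 0.8 or 1.0 | same as a | about 0.00 | 4.8% to 5.2% |
| 1.0 | 0.5 | -0.50 | 21% to 42% |
| 0.5 | 1.0 | +0.50 | 22% to 42% |
| 0.8 | 0 | -0.80 | 45% to 81% |
| 0 | 0.8 | +0.80 | 46% to 81% |

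Ranges run over the three correlations (and, in the first row, the three effect sizes). The fourth row bears on the primary objective: an acute increase that has gone by Week 8 appears as a decrease of the same size.

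**6. Power of the Week 8 arm comparison.** Noncentral t with 30 degrees of freedom and noncentrality d / √(2/16) = 2.83d:
- d = 0.5: 28%
- d = 0.8: 59%
- d = 1.0: 78%

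If 80% imaging and 20% drop-out both applied (an assumption), 40 × 0.8 × 0.8 = 25.6, about 13 per arm. Power would then be about 23%, 50% and 69%.

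**The case against.** The strongest reply is that the analysis section never specifies an arm-by-time interaction. It lists pre/post and active/placebo as separate comparisons, and the primary ANOVA has no time factor. So a valid arm comparison is already in the plan, and all that is missing is a definition of pre-treatment. The first part stands: the active versus placebo comparison and the ANOVA are sound at either scan. But the first objective does specify change compared between the arms, for the primary outcome, and the schedule has no scan that could make that change a drug effect. That is a wrong target of estimation, and a definition alone does not cure it.

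A second reply is that a pre-dose acquisition may be intended in the Week 2 session. No section describes one, and Aim 1 places imaging after dosing. If one is intended, the plan has to say so.

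A third reply is that exact cancellation needs s = a. The two exposures differ: a single dose imaged at its peak, against the end of a 6-week escalating regimen in divided doses. This stands, and the documents give no reason to expect equality. The contrast is still s - a in every case.

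Finally, the power figures assume one scalar outcome without correction, whereas the planned imaging analysis is voxelwise with family-wise correction. That is fair, and the figures are an illustration only.

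**Conclusion.** The point holds in limited form. With the two scheduled scans, a between-arm comparison of pre- to post-treatment change estimates s - a. It equals the sustained effect only if there is no acute effect, which is contrary to the trial's primary hypothesis. This rests on the schedule and on randomisation. The effect sizes, correlations and power figures are assumptions, and power would be lower with fewer Week 8 scans or with family-wise correction.

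A reader might infer more than the documents support:
- *That the primary imaging test is invalid.* The arm comparison at Week 2, including the ANOVA without a time factor, is valid. The fault is in the change wording of the objective and of the fMRI comparison list.
- *That any lasting effect cancels to zero.* That happens only if s = a.
- *That a negative contrast is an error in sign.* It is a correct estimate of sustained minus acute, and misleads only if labelled the sustained effect.
- *That the exploratory correlations with treatment response are affected.* No section says they use the change between scans.
- *That the plan commits to Week 8 minus Week 2 for the 6-week effect.* It leaves the scans unnamed.

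**What to change.** In the first objective (Purpose) and in the fMRI paragraph of Data Analysis and Statistical Considerations, replace the pre/post wording with two arm comparisons: DHEA versus placebo at the Week 2 scan (acute, primary) and DHEA versus placebo at the Week 8 scan (sustained). State that the active versus placebo comparison and the primary ANOVA use the Week 2 scan for the primary outcome. Do not subtract the Week 2 scan, or adjust for it, when estimating the Week 8 effect, because it is measured after randomisation and on drug. If a change score is reported, label it sustained minus acute. If a pre-dose scan is in fact planned, add it to the Schedule of Events and name it as the baseline.

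The main change costs only wording and needs no new scans. The small downside is that the Week 8 comparison has no within-person baseline to reduce its variance, but the present design provides none.
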